### 7.3. Adverse Events

An adverse event (AE) is defined as any untoward medical occurrence associated with the use of a drug in humans, whether or not considered drug related. An adverse event could therefore be any unfavorable and/or unintended sign (including abnormal laboratory findings), symptom, or disease temporally associated with the use of the drug, whether or not considered related to the drug. This definition includes inter-current illnesses or injuries, and exacerbation of pre-existing conditions.

An unexpected adverse event is an adverse event that is not identified in nature, severity, or frequency in the current Investigator's Brochure, or that is of greater severity than expected based on the information in the Reference Safety Information listing within the Investigator's Brochure.

All adverse events occurring in subjects who have been treated with CCX140-B will be recorded in the EDC system and will be reported in accordance with regulatory requirements. Adverse events reported prior to commencement of administration of study medication will be considered

pre-treatment events. If subject stops taking CCX140-B, adverse event reporting should be continued as long as study is active.

All adverse events will be monitored until resolution or, if the adverse event is determined to be chronic, until a cause is identified. If an adverse event remains unresolved at the conclusion of the study, a clinical assessment will be made by the Investigator and the Sponsor's Medical Monitor to determine whether continued follow-up of the adverse event is warranted.

### **7.3.1. Adverse Event Severity Assessment**

The severity of each adverse event will be determined by the investigator using the following scale:

- Mild (Grade 1): no limitation of usual activities
- Moderate (Grade 2): some limitation of usual activities
- Severe (Grade 3): inability to carry out usual activities
- Life-threatening (Grade 4): an immediate risk of death
- Death (Grade 5)

### **7.3.2. Causality Assessment**

The relationship of CCX140-B to an adverse event will be determined by the Investigator and Sponsor based on the following definitions:

- Probably Not Related: the adverse event was more likely explained by causes other than study drug CCX140-B.
- Possibly Related: there is evidence for a reasonable possibility that study drug CCX140-B administration caused the adverse event.

### **7.3.3. Serious Adverse Events**

A serious adverse event (SAE) is defined as any untoward medical occurrence that at any dose:

- Results in death;
- Is life-threatening (i.e., the subject was, in the opinion of the Investigator, at immediate risk of death from the event as it occurred);
- Requires or prolongs hospitalization;
- Results in persistent or significant disability or incapacity;
- Is a congenital anomaly or birth defect;
- Is an important and significant medical event that, based on appropriate medical judgment, may jeopardize the subject and/or may require medical or surgical intervention to prevent one of the other outcomes defining serious.

Elective surgery already known during screening to occur in the course of the study, and elective hospitalizations for convenience of the subject which are clearly unrelated to any medical condition, and agreed upon between the Investigator and the subject, will not have to be reported

as SAEs. Hospital stays on the evening of Day 1 (or beyond) will also not be considered an SAE, unless other SAE criteria are met.

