7. PK samples are to be collected from time 0 through 6 hours (0, 0.5, 1, 2, 3, 4 & 6) on study day 1 and on the relevant study day for each dose escalation (time 0 occurs immediately before the 1st dose and subsequent samples are collected at 0.5, 1, 2, 3, 4 & 6 hours after dosing and at least 2 weeks after the subject has completed dose escalation/adjustment and is receiving a continuous stable dose. Subjects can eat 1 hour after the time 0 blood draws have been completed (immediately after the 1 hour blood draw).
8. Medications taken up to 12 weeks prior to screening should be captured as concomitant medications. Prior treatment with rituximab or other anti-CD20 monoclonal antibodies and corresponding levels of CD20+ B cells need to be recorded up to 1 year prior to screening. Eligible patients who have entered the study on a continuous cycle therapy of rituximab or other anti-CD20 monoclonal antibodies need to remain on an unchanged therapy at a dosing interval that has been documented to achieve continuous B cell depletion for the given patient unless prohibited due to safety considerations. Their levels of CD20+ B cells that are routinely evaluated per standard of care with anti-CD20 monoclonal antibody therapy need to be recorded throughout the study.

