### **7.3.7. Serious Adverse Event Reporting**

Any serious adverse event occurring from screening through the end of the treatment period, whether or not considered study related, will be reported immediately (within 24 hours) to the Safety team. Reporting is done by completing the SAE form in the EDC system. If it is not possible to access the EDC system, the Investigator will send an email to the appropriate regional clinical safety mailbox (see information below) or call their regional SAE hotline and fax the completed SAE report form within 24 hours of awareness. When access to the EDC system is resumed, the SAE information should be entered as soon as possible. Contact details are as follows:

[REDACTED] Clinical Safety

Telephone: [REDACTED] or [REDACTED] or [REDACTED]  
Facsimile: [REDACTED] or [REDACTED] or [REDACTED]  
e-mail: [REDACTED]

Any medication or other therapeutic measures used to treat the event, in addition to the outcome of the adverse event, will be recorded in the EDC system.

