### **7.5.1. Dose Modification / Stopping Rules for the Overall Study**

A dose will be considered as potentially exceeding the maximum tolerated dose and consideration will be given for stopping the study should any of the following events occur:

- 2 or more subjects with QTcF prolongation  $\geq$  450 msec and an increase from baseline of  $\geq$  30 msec, based on triplicate 12-lead ECGs that is not otherwise explained
- 2 or more subjects with clinically significant hemolytic anemia, defined as hemoglobin that has declined from baseline by at least 2 grams/deciliter and is less than or equal to 8 g/dL and is assessed by the investigator and is not otherwise explained
- 2 or more subjects with bilirubin greater than 3 times upper limit of normal, and not ascribable to Gilbert's disease
- 2 or more subjects with new motor neuropathy or sensory neuropathy that limits instrumental activities of daily living and is assessed by the Investigator as clinically significant
- 2 or more subjects who require dose reduction or discontinuation due to adverse events assessed as possibly related to Study Drug, where the adverse events are medically similar in the same System Organ Class based on MedDRA criteria.

If a dose is assessed to be above the maximally tolerated dose, dosing and dose escalation will be limited to the next lower dose.

A Safety Review Committee (SRC) comprising the Study Director, Medical Monitor, Clinical Pharmacologist, at least one external expert nephrologist, and Study Statistician will review all safety events described in the stopping rules and all serious adverse events as they occur. The SRC will periodically review all adverse events and all laboratory abnormalities. The SRC may declare a dose to be above the maximally tolerated dose based on the defined rules, or based on other considerations.

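### Protocol Section 7.3.3 exempts hospital stays from the evening of Day 1 onward without limiting reason or duration, which contradicts its own hospitalization criterion for a serious adverse event

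*Protocol*

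**What the plan says.** Protocol Section 7.3.3 opens: "A serious adverse event (SAE) is defined as any untoward medical occurrence that at any dose" meets one of six criteria. The third is "Requires or prolongs hospitalization", with no restriction on time or reason. The last is a judgment criterion: "Is an important and significant medical event that, based on appropriate medical judgment, may jeopardize the subject", or that may need intervention to avert one of the other outcomes.

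The section then lists exemptions. One is elective surgery already known at screening. Another is "elective hospitalizations for convenience of the subject which are clearly unrelated to any medical condition", if the investigator and subject have agreed to it. The last is the sentence at issue: "Hospital stays on the evening of Day 1 (or beyond) will also not be considered an SAE, unless other SAE criteria are met".

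Four things depend on SAE status:

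- **Reporting:** Protocol Section 7.3.7 requires SAEs to reach the safety team within 24 hours.
- **Classification:** Protocol Section 7.3.4 defines both SARs and SUSARs as kinds of SAE.
- **Oversight:** Protocol Section 7.5.1 has the SRC review "safety events described in the stopping rules and all serious adverse events as they occur".
- **Analysis:** SAP Section 3.6.1 counts subjects and events for SAEs and TESAEs.

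**The concern.** The section names hospitalization as sufficient for seriousness and then, a few lines later, says that hospital stays from the evening of Day 1 are not serious unless something else makes them so. In ordinary usage *other* criteria means criteria other than hospitalization. *Or beyond* sets no limit on how long the exemption runs.

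The hospitalization criterion is useful because it needs no judgment: the subject was admitted or was not. If the exemption is followed as written, that test is replaced after first dosing by an investigator's opinion on medical importance. Two sites could then classify the same admission differently, and only one of them would send a 24-hour report. SAP Sections 1 and 6 restrict the safety summaries for an abbreviated report, so the SAE counts carry more of the weight.

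**Working it through.** The plan gives no figure to reproduce here. The check sets the texts against each other.

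**1. What the sentence removes.** The six criteria are death, threat to life, hospitalization, disability, congenital anomaly and important medical event. Read literally, the exemption leaves five able to act from the evening of Day 1. Only an event whose sole qualifying criterion is hospitalization changes status.

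**2. How the three exemptions are limited.**

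| Exemption in Section 7.3.3 | Limit by reason | Limit by time |
|---|---|---|
| Elective surgery | Elective, planned | Known at screening |
| Convenience admission | Unrelated to any medical condition, agreed in advance | None needed |
| Stay from the evening of Day 1 | None stated | Start stated, no end |

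The third is joined to the others by *also*, so it adds to them, but it carries neither kind of limit.

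**3. Whether a scheduled stay explains it.** The Time and Events Table (footnote 7) says "PK samples are to be collected from time 0 through 6 hours", and Section 6.2 likewise ends Day 1 sampling at 6 hours. Appendix A has the 24-hour urine collected at home. Section 7.6 has subjects take the tablets themselves. No visit in Section 6 includes an overnight stay.

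**4. Whether another section limits it.** Sections 7.3 and 7.3.7 do not mention hospital stays. SAP Section 3.6.1 uses the SAE label without defining it. Nothing found in either document narrows the sentence.

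**5. One case traced both ways.** Suppose a subject is admitted in Week 6 with an infection that is not life-threatening, causes no lasting disability, and is not judged an important medical event.

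| Step | Hospitalization criterion applied | Exemption read literally |
|---|---|---|
| Recorded as an AE (Section 7.3) | Yes | Yes |
| 24-hour report (Section 7.3.7) | Yes | No |
| Can be a SAR or SUSAR (Section 7.3.4) | Yes | No |
| SRC review as an SAE when it occurs (Section 7.5.1) | Yes | No |
| SRC periodic review of all AEs (Section 7.5.1) | Yes | Yes |
| SAE and TESAE counts (SAP Section 3.6.1) | Yes | No |

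The AE listing fields in SAP Section 3.6.1 show SAE categories where they apply but have no separate item for admission. A reader of that listing would not see that this subject was hospitalized.

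**6. Size, as an illustration.** SAP Section 2.2.4 plans 6 subjects in the first stage and 13 in total. If one subject has such an event and no other SAE, SAE incidence moves by 1/13 = 0.077 (7.7 percentage points) at the planned maximum, or 1/6 = 0.167 (16.7 points) in the first stage. Enrolment was stopped (SAP Sections 1 and 6) and the actual number is not given. With 13 as the ceiling, the shift for one such subject is at least 7.7 points.

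**The case against.** The strongest defence is that the sentence was meant for a non-medical stay: a subject kept overnight after first dosing and 6-hour sampling as a precaution or for travel, perhaps for more than one night. An SAE must be an untoward medical occurrence, and a bed for the night is not one. The neighbouring exemptions concern planned or non-medical admissions, and a precautionary stay fits neither of them exactly, so the sentence could have had its own purpose. This reading is possible, and that no overnight stay is scheduled does not prove none was foreseen. But the text does not say it. If only stays without an untoward event were meant, the proviso about other SAE criteria would have little to do.

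Three stronger inferences are tempting, and the documents do not support them.

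- **That the hospitalization criterion is cancelled for the whole study.** It remains listed. SAE reporting starts at screening, and admissions before the evening of Day 1 are not touched. After that, an admission meeting any other criterion is still an SAE, and the important-medical-event criterion can capture many of them, though by judgment.
- **That admissions would escape the SRC.** All AEs in treated subjects are recorded, and the SRC goes through all of them at intervals. Some would arrive sooner. The Synopsis has the SRC review events under the dose modification rules as they occur (Section 7.5.1 refers to the stopping rules). Anaemia, hemolysis and rising creatinine have rows in Table 2 of Section 7.5. What is lost is review as an SAE at the time.
- **That 7.7 points estimates an error.** It is arithmetic on a hypothetical subject.

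**Conclusion.** Section 7.3.3 contradicts itself. As written, it lets an AE whose only serious feature is admission be classed as non-serious at any time from the evening of Day 1. The consequence is loss of the four SAE-dependent steps for that group of events, with a slower and judgment-dependent route in their place.

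This rests on reading *other* as excluding hospitalization, and on sites applying the sentence as it stands. If every site already takes it to mean non-medical stays, nothing is misclassified and only the wording is at fault. The documents do not show which reading sites used, and they show no event that was missed. The matter should be put right because it concerns safety reporting and the correction is small.

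**What to change.** Delete the sentence. Alternatively, limit it to hospital stays made solely for study procedures or logistics with no untoward medical occurrence. In either case remove *or beyond*. Any SAE completion guidance should match. The SAP text needs no change, because its counts follow the SAE label.

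The documents do not show whether the database has been locked. If it has not, ask sites which recorded AEs involved a hospital admission on or after Day 1, compare each with the hospitalization criterion, and report any that should have been SAEs.

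The cost is one sentence, a short query covering at most 13 subjects, and possibly a few more SAE forms.

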#### 7.3.4. SARs and SUSARs

A serious adverse reaction (SAR) is defined as an SAE for which there is at least a reasonable possibility that the study drug CCX140-B caused the event.

A suspected unexpected serious adverse reaction (SUSAR) is defined as an SAE for which there is at least a reasonable possibility that the study drug CCX140-B caused the event, and the SAE is ‘unexpected’, i.e., not described in terms of nature, severity, or frequency in the Reference Safety Information within the current Investigator’s Brochure.

‘Reasonable possibility’ means that there is evidence to suggest a causal relationship between the study drug and the adverse event. Within the reporting requirements, the following examples illustrate the types of evidence that would suggest a causal relationship:

- A single occurrence of an event that is uncommon and known to be strongly associated with drug exposure (e.g., angioedema, hepatic injury, Stevens-Johnson Syndrome);
- One or more occurrences of an event that is not commonly associated with drug exposure, but is otherwise uncommon in the population exposed to the drug (e.g., tendon rupture);
- An aggregate analysis of specific events observed in a clinical trial (such as known consequences of the underlying disease or condition under investigation or other events that commonly occur in the study population independent of drug therapy) that indicates those events occur more frequently in the drug treatment group than in a concurrent or historical control group.

Events related to the underlying disease, such as relapses or worsening of disease will not be considered as SUSARs, unless there is a reasonable possibility that CCX140-B use was associated with these events.

#### 7.3.5. Pregnancies

Any pregnancies that occur in female subjects or partners of male study subjects must be reported to [REDACTED] Clinical Safety within 24 hours of awareness to the contacts details outlined in [Section 7.3.3](#). An exposure in Utero form will then be forwarded for completion as soon as possible. All pregnancies must be followed up until conclusion and the outcome of the pregnancy reported within 24 hours of awareness to [REDACTED] Clinical Safety. Should the outcome of the pregnancy meet criteria for an SAE, it should be reported as indicated in [Section 7.3.3](#).

#### 7.3.6. Special Situation Reporting

Special situation reports include reports of overdose, misuse and abuse of the IMP:

- Overdose: refers to the administration of a quantity of a medicinal product given per administration or cumulatively (accidentally or intentionally), which is above the maximum recommended dose according to the protocol. Clinical Judgment should always be applied. In cases of a discrepancy in the drug accountability, overdose will be established only when it is

clear that the subject has taken excess dose(s) or the investigator has reason to suspect that the subject has taken additional dose (s).

- Misuse: refers to situations where the medicinal product is intentionally and inappropriately used not in a way that is not in accordance with the protocol instructions or local prescribing information and may be accompanied by harmful physical and/or psychological effects.
- Abuse: is defined as persistent or sporadic, intentional excessive use of a medicinal product, which is accompanied by harmful physical or psychological effects.
- Medication Error: Medication error is any unintentional error in the prescribing, dispensing or administration of a medicinal product by a healthcare professional, patient or consumer, respectively. The administration or consumption of the unassigned treatment and administration of an expired product are always reportable as medication errors, cases of subjects missing doses of investigational product are not considered reportable as medication error.

All special situation reports must be reported on the special situations report form and forwarded to [REDACTED] Clinical Safety within 24 hours.

All adverse events (AEs) associated with these special situation reports should be reported as AEs or SAEs at the same time using the AE eCRF and/or the SAE report form. Details of the symptoms and signs, clinical management and outcome will be reported, when available.

### **7.3.7. Serious Adverse Event Reporting**

Any serious adverse event occurring from screening through the end of the treatment period, whether or not considered study related, will be reported immediately (within 24 hours) to the Safety team. Reporting is done by completing the SAE form in the EDC system. If it is not possible to access the EDC system, the Investigator will send an email to the appropriate regional clinical safety mailbox (see information below) or call their regional SAE hotline and fax the completed SAE report form within 24 hours of awareness. When access to the EDC system is resumed, the SAE information should be entered as soon as possible. Contact details are as follows:

[REDACTED] Clinical Safety

Telephone: [REDACTED] or [REDACTED] or [REDACTED]  
Facsimile: [REDACTED] or [REDACTED] or [REDACTED]  
e-mail: [REDACTED]

Any medication or other therapeutic measures used to treat the event, in addition to the outcome of the adverse event, will be recorded in the EDC system.

#### Follow-Up Reports

The investigator must continue to follow the subject until the SAE has subsided or until the condition becomes chronic in nature, stabilizes (in the case of persistent impairment), or the subject dies.

Within 24 hours of receipt of follow-up information, the investigator must update the SAE form electronically in the EDC system for the study and submit any supporting documentation (e.g., subject discharge summary or autopsy reports) to [REDACTED] Clinical Safety via fax or e-mail. If it is not possible to access the EDC system, refer to the procedures outlined above for initial reporting of SAEs.

SAE reporting should continue for 90 days after stopping study drug. The Sponsor should be notified if the investigator becomes aware of any SAE that occurs after the end of the AE reporting period, if they believe that an event is related to the prior study drug treatment.

The Sponsor or its representatives will report all SUSARs to national health authorities and ethics committees in an expedited manner in accordance with Clinical Trial Directive, Articles 16 and 17, ICH Guideline E2A and ENTR CT3 on the reporting of all SUSARs.

#### 7.4. Study Completion and Withdrawal

The Week 12 visit will be the final treatment day and the week 16 visit will be the last Study Day for all subjects, except for those participating in the Open-Label Extension (last visit will be Week 52). Procedures for this day will be completed per the [Time and Events Table](#). Each subject's condition will be evaluated by the Investigator at the end of the clinical trial and appropriate standard of care medical treatment will be provided to all subjects as needed. For early withdrawals from the study, the procedures for the Early Termination visit will be performed, including blood draws during the termination visit and again 7 & 14 days after the final dose, when possible. The clinical trial will be terminated early if there is a safety concern.

#### 7.5. Dose Modification Rules

**Table 2: Dose Modification Rules for Individual Subjects**

Assessment	Event	Timing	Response
Serum Creatinine	50% increase from baseline value	If confirmed by repeat measurement after 2 weeks	If confirmed by repeat measurement after 2 weeks
Urine Protein:Creatinine ratio (UPCR)	If baseline UPCR < 6.0 g/g an increase of > 3.0 g/g; if UPCR $\geq$ 6.0 g/g an increase of 50%	If confirmed by repeat measurement after 2 weeks	If confirmed by repeat measurement after 2 weeks
ALT, AST	ALT or AST $\geq$ 8x ULN	Confirmed within 72 hours (ALT, ASP, ALP and Total Bilirubin should all be re-tested)	Consider Discontinuation of Treatment
ALT, AST	ALT or AST $\geq$ 5x ULN	Confirmed within 2 weeks (ALT, ASP, ALP and Total Bilirubin should all be re-tested)	Consider Discontinuation of Treatment
ALT, AST, Total	ALT or AST $\geq$ 3x	Confirmed within 72	Consider Discontinuation of

Bilirubin and INR	ULN and Total Bilirubin > 2 ULN or INR > 1.5	hours (ALT, ASP, ALP, Total Bilirubin and INR should all be re-tested)	Treatment
ALT, AST	ALT or AST $\geq$ 3x ULN with the appearance of fatigue, nausea, vomiting, right upper quadrant pain or tenderness, fever, rash and /or eosinophilia (>5%)	Confirmed within 72 hours (ALT, ASP, ALP and Total Bilirubin should all be re-tested)	Consider Discontinuation of Treatment
Hemolysis	Clinical diagnosis of hemolysis in the judgment of the investigator, based on elevation of LDH, elevation of reticulocyte count, elevation of bilirubin and or other laboratory indications.	Halt treatment then reassess after 1 week	If normalized, continue to treat at reduced dose, defined as the next lower dose. Otherwise, contact Medical Monitor to discuss next steps
Anemia	Hemoglobin reduced from baseline by $\geq$ 2 g/L and deemed clinically significant by the PI	Halt treatment then reassess after 2 weeks	If normal, continue to treat at reduced dose, defined as next lower dose. Otherwise, contact Medical Monitor to discuss next steps
Reticulocyte Count	Increase in reticulocyte count by $\geq$ 2% (absolute) from baseline that is not otherwise explained	Halt treatment then reassess after 2 weeks	If within normal range for the hematocrit, continue to treat at reduced dose, defined as next lower dose. Otherwise, contact Medical Monitor to discuss next steps
Peripheral Neuropathy	$\geq$ moderate symptoms limiting (limiting instrumental activities of daily living or asymptomatic (based on diagnostic evaluation only) and deemed clinically significant by the investigator	Halt treatment then reassess after 2 weeks	Contact Medical Monitor to discuss next steps
Other Clinically Significant Events	Any adverse events assessed as moderate, related to study drug, and clinically significant	Halt treatment then reassess after 2 weeks	Contact Medical Monitor to discuss next steps

